Systemic formulations of cyclosporine are known to have contraindications related to St. John's Wort and medicines that are substrates of P-gp or organic anion-transporting polypeptide (OATP). Prior studies of L-CsA have demonstrated negligible serum levels and no accumulation over time of cyclosporine. No potential drug interactions during clinical studies have been reported. Drug-drug interactions are unlikely because the systemic cyclosporine exposure with L-CsA is much lower than for approved therapeutic doses of oral and IV cyclosporine.

Based on clinical experience to date with L-CsA, there are no special precautions for administration of L-CsA in clinical studies using the drug product and device component. Pharmacokinetic studies have shown that the systemic cyclosporine exposure with L-CsA is much lower than for approved therapeutic doses of oral and IV cyclosporine. Consult oral or IV cyclosporine prescribing information for various precautions associated with the higher systemic exposures that may occur after oral or IV dosing of cyclosporine.

Patients who are given L-CsA may also receive other inhaled medications. When L-CsA is administered concomitantly with other inhaled medicinal products, the order of inhalation should be as follows: inhaled bronchodilators, inhaled corticosteroids, inhaled antifungals/ antibiotics, and then inhaled L-CsA. L-CsA inhalation should occur at least 1 hour after administration of any other inhaled medications.

No event associated with overdose has been reported in any L-CsA clinical trial to date. As has been demonstrated through PK studies, systemic exposure is significantly low compared with the approved therapeutic doses of oral or IV cyclosporine.

COVID-19 considerations: At this time, it is unknown if specific patient populations are at higher risk of SARS-CoV-2 infection. Furthermore, the medical surveillance of transplanted patients is already based on specific precautions typical to all patients taking immunosuppressive agents. The medical value of this trial remains unchanged.

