10.1.2 Immunosuppression

Immunosuppressive therapy is permitted and will be performed to centers' standard regimen.

The use of different formulations of aerosolized Cyclosporine A other than L-CsA is strictly prohibited during the complete clinical trial period. Systemic administration of CsA is permissible if medically necessary at the discretion of the investigator.

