12.1.6.2 Pharmacokinetic Parameters

Whole blood samples for determination of cyclosporine A will be collected at Visit 1 pre-dose, directly after end of inhalation; and 15, 30, and 45 minutes (+/- 5 minutes), and 1, 1.5, 2, and 4

hours (+/- 15 minutes) after end of inhalation for determination of C_{max} , t_{max} , and AUC_{0-4h} . PK analysis will be performed in a central laboratory (CCI [REDACTED]).

All sites will be provided with specific Laboratory Kits for collecting the PK blood samples. Blood should be collected into the respective pre-labelled K2-EDTA Tubes and should be stored at -20°C immediately after collection until shipment to the central laboratory.

Instruction on handling, processing, storage and shipment are in detailed described in the Laboratory Manual for Pharmacokinetic Blood Sampling.

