12.1.6.3 Cyclosporine A Whole Blood Trough Levels

A whole blood sample for the determination of cyclosporine A trough level will be collected at Visit 2 to Visit 5 at each on-site visit. The sample should be collected 15 minutes before inhalation. The trough levels of CsA at visit 2 to 5 will be analysis will be performed in a central laboratory (CCI [REDACTED]).

All sites will be provided with specific Laboratory Kits for collecting the PK blood samples. Blood should be collected into the respective pre-labelled K2-EDTA Tubes and should be stored at -20°C immediately after collection until shipment to the central laboratory.

Instruction on handling, processing, storage and shipment are in detailed described in the Laboratory Manual for Pharmacokinetic Blood Sampling.

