14.2.5 Pharmacokinetic Variables

The statistical analysis will be performed as a valid case analysis including all patients of the FAS. No subgroup analysis is planned.

Descriptive statistics will be used by the **CCI** (N, arithmetic means, standard deviation, geometric means, geometric coefficient of variation, medians, minimum and maximum) and will be presented for all PK parameters indicated in [Section 8.1.6](#), separately for each treatment by using the **CCI**.

The plasma concentration levels in the **CCI** are measured using a validated LC-MS / MS method. The procedure for validation and the acceptance limits are based on the requirements of the EMA Guideline (Guideline on bioanalytical method validation (EMEA / CHMP / EWP / 192217/2009 Rev. 1 Corr. 2 **), July 2011).

The statistical analysis will be carried out on a log scale for $AUC_{0-4\text{ h}}$ and C_{\max} -values, while t_{\max} and trough levels will be evaluated on a linear scale. Analyses of variance will be performed to compare the treatment groups.

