### 10.2.2 Full Analysis Set

The Full Analysis Set (FAS) is defined as all randomized patients for whom a baseline and at least one post-baseline measurement of an efficacy outcome measure, i.e., for spirometry or quality of life measures (Section 8.5), is available. For spirometry measures, baseline will correspond to the assessment at randomization visit (Visit 1) prior to inhalation of IMP. Patients will be analyzed according to the treatment group to which they were randomized.

A BDRM will determine if patients should be excluded from the FAS in cases of significant protocol deviations that preclude an assessment of treatment efficacy (e.g., randomized patients not suffering from the condition under investigation). Any exclusion of patients from the FAS will require individual justification.

The primary analysis of all efficacy endpoints will be performed using the FAS.

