### **14.2 CsA Pharmacokinetics**

PK analyses will be carried out using SAS® software, Version 9.4 or later. Descriptive statistics (N, arithmetic means, standard deviation, geometric means, geometric coefficient of variation, medians, minimum and maximum) will be presented for all PK parameters indicated in section 8.4 including Whole blood trough level parameter (Cyclosporine A Concentration) at Weeks 2, 4, 8, and 12, separately for each treatment group. A figure with overlaying individual pharmacokinetic concentration-time profiles will be presented for plasma concentrations after end of inhalation per treatment group.

---

The statistical analysis will be carried out on a log scale for  $AUC_{0-4\text{ h}}$  and  $C_{\max}$ -values, while  $t_{\max}$  and trough levels will be evaluated on a linear scale.

Analyses of variance will be performed to compare the treatment groups with regards to  $AUC_{0-4\text{ h}}$  and  $C_{\max}$ . This will include the computation of 95% confidence intervals for the between-group differences.

The statistical analysis will be performed as a valid case analysis including all patients of the FAS.

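### SAP 14.2 compares cyclosporine PK by arm in all FAS patients without separating users of permitted systemic cyclosporine, so if users enrol the arm summaries mix systemic with inhaled drug (minor, cheap to improve)

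*SAP*

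**What the plan says.** SAP 14.2 gives descriptive statistics for AUC0-4h, Cmax, tmax and the trough levels by treatment group. AUC0-4h and Cmax are analysed on the log scale: "Analyses of variance will be performed to compare the treatment groups with regards to" those two parameters, with 95% confidence intervals for the group differences. The population is fixed by "The statistical analysis will be performed as a valid case analysis including all patients of the FAS". Protocol 14.2.5 uses the same population and adds "No subgroup analysis is planned". Neither text names a covariate, a pre-dose correction or a split by systemic cyclosporine use.

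Protocol 10.1.2 says of co-medication: "Systemic administration of CsA is permissible if medically necessary at the discretion of the investigator". No exclusion criterion in Protocol 9.2 bars users, and Protocol 8.3 provides no stratification.

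On sampling, Protocol 12.1.6.2 says "Whole blood samples for determination of cyclosporine A will be collected at Visit 1 pre-dose, directly after end of inhalation" and then at times up to 4 hours. Protocol 12.1.6.3 says "A whole blood sample for the determination of cyclosporine A trough level will be collected at Visit 2 to Visit 5". On relative size, Protocol 6.1.5 says "the systemic cyclosporine exposure with L-CsA is much lower than for approved therapeutic doses of oral and IV cyclosporine".

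**The concern.** Inhaled and systemic cyclosporine are the same molecule, and the plan describes no means of telling them apart in a blood sample. On the protocol's own account of relative exposure, the level in a patient on a therapeutic systemic dose would be mostly systemic drug. In an arm of 8, one such patient can move a geometric mean or a mean trough appreciably.

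PK is a secondary assessment. Protocol 6.1.5 describes it as the first PK information in this population, intended to support further development in the indication. That purpose needs an interpretable estimate of what the inhaled doses contribute, and the only planned arm-level analysis may not give one.

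The plan already collects what is needed to separate users. There is a Visit 1 sample before any study drug, a concomitant-medication record starting 30 days before randomization (Protocol 10.1), and an immunosuppressant flag (SAP 15.3). None of these is linked to the PK analysis.

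**Working it through.** The plan has no PK figure to reproduce. The sample size of 3 × 8 = 24 rests on feasibility (SAP 9.2), so the check is an illustration.

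**Inputs from the documents:** 8 patients per arm; log-scale comparison of AUC0-4h and Cmax; 95% intervals; no stratification.

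**Assumptions, not in the documents:** typical inhaled exposure of 1 unit at 10 mg and 0.5 at 5 mg (true ratio 2.0); systemic drug adding k = 3, 10 or 30 units in a user; between-patient log-SD of 0.5.

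**Ratio.** With n10 and n5 users in the two active arms,

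ratio = 2 × (1 + k)^(n10/8) × (1 + 2k)^(−n5/8).

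For example, one user in the 5 mg arm at k = 3 gives 2 × 7^(−1/8) = 1.57.

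| Users (10 mg, 5 mg) | k = 3 | k = 10 | k = 30 |
|---|---|---|---|
| 0, 0 | 2.00 | 2.00 | 2.00 |
| 0, 1 | 1.57 | 1.37 | 1.20 |
| 1, 0 | 2.38 | 2.70 | 3.07 |
| 1, 1 | 1.86 | 1.84 | 1.84 |
| 0, 2 | 1.23 | 0.93 | 0.72 |
| 2, 0 | 2.83 | 3.64 | 4.72 |

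The ratio falls below 1 when 1 + 2k exceeds 2^(8/n5). With two users in the 5 mg arm only, that means k > (16 − 1)/2 = 7.5. With one user it means k > (256 − 1)/2 = 127.5.

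**Chance of imbalance.** With 2 users among the 16 active patients, both fall in one arm with probability 2 × C(8,2)/C(16,2) = 56/120 = 47%.

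**Precision.** Without users, the factor by which the 95% limits lie above and below the ratio is exp(t × 0.5 × √(1/n1 + 1/n2)). For 8 v 8 this is exp(2.145 × 0.5 × 0.5) = 1.71. In simulation (40,000 trials per setting), one user in each arm widens the median factor to 2.3, 3.2 and 4.6 for k = 3, 10 and 30.

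**Coverage and medians, same simulation.** With one user in one active arm, the interval covers 2.0 in about 95% or more of trials, because it widens as the estimate shifts. The ratio of medians is about 1.8 (user in the 5 mg arm) or 2.2 (user in the 10 mg arm). With two users in one arm only, coverage is about 90–96% and the ratio of medians about 1.6 or 2.5.

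**Troughs.** On the linear scale, a user whose systemic trough is T adds about T/8 to the mean of an arm of 8.

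**The case against.** The strongest reply is that the harm depends on facts the documents do not give. If nobody takes systemic cyclosporine, the plan is fine. This stands, and it is why every figure above is conditional.

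Second, total cyclosporine on top of standard care is a legitimate quantity. The PK objective in SAP 7 is framed as add-on to standard care, and Protocol Appendix II refers to monitoring systemic levels. This also stands, and the all-FAS summary should stay. It does not make that summary an estimate of inhaled exposure.

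Third, the placebo arm helps. For troughs, active minus placebo removes background systemic drug in expectation if use does not differ by arm. In arms of 8, however, one extra user on one side shifts the difference by about T/8.

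Fourth, medians, overlaid individual profiles and the medication listing are planned, and a split could be added later as an unplanned analysis. These can reveal the mixing, but they give no non-user ratio with an interval, and a later exclusion in such small arms invites challenge.

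A reader might go further and infer that the dose order will be reversed or the intervals will mislead. The documents do not support that. Within the range of k used here, reversal needs two users in the 5 mg arm and none in the 10 mg arm, with k above 7.5, and the intervals mostly still cover the true ratio.

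A reader might also infer that a patient with a full Day 1 profile who leaves before Week 2 is certainly lost, because the FAS needs "at least one post-baseline measurement of an efficacy outcome measure" and SAP 8.5 lists Weeks 2 to 12. That is not settled. Protocol 13.2.2 repeats spirometry about 1 hour after the first dose, and SAP 10.2.2 sets the spirometry baseline before inhalation, so the 1-hour value may qualify. The text is ambiguous.

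**Conclusion.** The gap is real and the point holds conditionally. Systemic cyclosporine is permitted, and the planned PK analysis does not distinguish users. If they enrol, the arm geometric means, the 10 mg to 5 mg ratio and the mean troughs mix two sources of drug.

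Under the stated assumptions, a single user in one active arm moves a true ratio of 2.0 to between 1.20 and 1.57, or to between 2.38 and 3.07. One user in each arm leaves the ratio near 1.85 but widens the interval factor from 1.71 to between 2.3 and 4.6. Two users in one arm only is the less favourable case, with ratios from 0.72 to 4.72. The damage is to the point estimate and the precision more than to coverage.

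The reach is limited. All analyses are exploratory (Protocol 14), no decision rule uses the ratio, and the primary safety and tolerability analysis is unaffected. This is a minor point and a cheap improvement.

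**What to change.** Revise SAP 14.2 and add an entry to the table in SAP 6:

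1. Before database lock, classify each patient as a systemic cyclosporine user or non-user before the first study dose, from the concomitant-medication record and the Visit 1 pre-dose level. State a rule for disagreement, for example user if either source is positive.
2. Report Day 1 PK and the 10 mg to 5 mg geometric mean ratio with its 95% interval in non-users. List users separately. Keep the all-FAS summary, labelled as total cyclosporine exposure.
3. Report troughs descriptively by whether systemic cyclosporine was in use at the sample, with that window defined before lock. Note that use may start after randomization, so this split is not a randomized comparison.

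As an optional clarification, define the PK set as patients who received study drug and have an evaluable concentration. This removes the ambiguity about early leavers.

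The cost is a SAP revision and a sentence in the study report explaining the difference from Protocol 14.2.5. No new data and no change to permitted medication are involved. The non-user analysis is smaller: with two users removed, the interval factor at log-SD 0.5 rises from 1.71 to 1.79 (7 v 7) or 1.80 (8 v 6).

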Assessments	
Clinical Trial Plan:
 
At total of 7 visits (Screening, Randomization (Week 0), Week 2, Week 4, Week 8, Week 12 (End of Treatment [EoT]) and Week 14 (End of Study [EoS]) will be performed during the clinical trial. AEs and concomitant medications will be recorded at all visits.
 
Screening: After informed consent has been obtained. Screening Visit procedures will be carried out to check general eligibility for participation up to 4 weeks prior to randomization. Blood will be drawn for safety profiles.
 
Visit 1, Week 0 (Baseline Visit, Randomization): Blood for baseline measures will be collected. Spirometry will be performed. A pregnancy test will be performed for all females of childbearing potential prior to randomization. A physical exam, including vital signs, will be performed. The CGI Questionnaire will be administered. The SF-36 Quality of Life Questionnaire will be administered. Patients will be randomized to study treatment and instructed on use of the L-CsA CCI. The first dose of IMP will be administered under observation and safety will be monitored. Spirometry will be repeated 1 hour \pm 20 min after completion of the first dose of IMP. Blood will be drawn for safety profiles and PK data at pre-dose. PK samples will be obtained directly after end of first inhalation, at 15, 30, and 45 minutes, and 1, 1.5, 2, and 4 hours after end of inhalation. If no tolerability issues are observed, patients will be permitted to leave the clinic. Patients will receive the full IMP supply for the 12 weeks treatment period. The second dose of IMP and all subsequent doses should be inhaled approximately 12 hours after the first dose.
 
Visit 2, Week 2: Spirometry will be obtained. Blood will be drawn for safety profiles and trough levels of CsA. A pregnancy test will be performed for all females of childbearing

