## 8.5 Exploratory Endpoints

The following measures of treatment efficacy will be analyzed as exploratory assessments:

- FEV1 % predicted, FEV1/FVC at randomization compared to Week 2, Week 4, Week 8, and Week 12
- SF-36 Quality of Life Questionnaire at Week 2, Week 4, Week 8, and Week 12
- Changes in the dose of corticosteroids and immunosuppressive therapy administered throughout trial duration

For efficacy assessments determined at post-baseline visits, measured values as well as change from baseline will be analyzed.

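### PK is analysed in the efficacy FAS and grouped as randomised: a wrongly dosed patient's exposure is filed under a dose not inhaled, and a valid Day 1 profile can be lost for reasons unrelated to PK

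*SAP*

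**What the plan says.** SAP 14.2 sets the PK population in one sentence: "The statistical analysis will be performed as a valid case analysis including all patients of the FAS". Protocol 14.2.5 has the same sentence. AUC0-4h and Cmax are compared between groups by analysis of variance on the log scale, with 95% confidence intervals.

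SAP 10.2.2 gives the FAS three features that matter here:

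- **Entry** depends on efficacy data. The set is "defined as all randomized patients for whom a baseline and at least one post-baseline measurement of an efficacy outcome measure" is available, for spirometry or quality of life, with a reference to SAP 8.5.
- **Grouping:** "Patients will be analyzed according to the treatment group to which they were randomized".
- **Exclusion** at the BDRM is possible for "significant protocol deviations that preclude an assessment of treatment efficacy", each with individual justification.

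SAP 10.2 and 11 name only the SAF, FAS and PPS. Only the SAF is grouped by treatment received (SAP 10.2.1). Protocol 14.1 says safety is analysed as treated and efficacy as randomised, and does not mention PK.

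The first-dose profile consists of a pre-dose sample and eight samples up to 4 hours after inhalation, all at Visit 1 (protocol 13.2.2).

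**The concern.** A concentration reflects the dose inhaled, not the dose assigned. Grouping as randomised is a sound rule for efficacy, but for PK it mislabels any patient who received another strength. That patient's adverse events would be tabulated under one dose and the exposure under another. Protocol 12.1 itself describes PK sampling under the assessment of safety, yet the analysis sits in the efficacy set, and the SAP gives no reason.

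Entry to the set also depends on something other than PK. The Cmax, tmax and AUC0-4h data are complete on Day 1, but whether they are analysed depends on an efficacy baseline, a post-baseline efficacy value and an efficacy-based review. Exit soon after the first dose may be related to tolerability, so a loss at that point need not be random. At stake is the description of exposure by dose in the first PK evaluation of L-CsA in this population (protocol 6.1.5).

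**Working it through.** **Inputs from the documents.** Three arms of 8; 3 × 8 = 24 agrees with SAP 9.2. That number rests on feasibility. No effect size, variability or dropout rate is given, so there is no sample-size formula to reproduce. The dose ratio R, the placebo contrast K, the CV and the exit rates below are assumptions, shown as ranges.

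**1. Misfiling between the 5 mg and 10 mg arms.** Let R be the true 10 mg/5 mg ratio of geometric means.

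- One patient randomised to 10 mg but given 5 mg: the 10 mg arm has seven values at level R and one at level 1, so the estimated ratio is R^(7/8). The reverse error, 5 mg assigned and 10 mg inhaled, raises the 5 mg mean by R^(1/8) and gives the same result.
- One swap, with one error in each arm: R^(6/8).

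| True R | One misfiled | One swap |
|---|---|---|
| 1.5 | 1.43 | 1.36 |
| 2 | 1.83 | 1.68 |
| 3 | 2.62 | 2.28 |

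Grouping by treatment received recovers R in every row.

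**2. Errors that involve placebo.** Let K be the factor by which the patient's value falls below the typical value of the arm in which it is filed. That arm's geometric mean drops by K^(1/8), which is 1.33, 1.53 or 1.78 for K = 10, 30 or 100. With R = 2:

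- A 10 mg patient given placebo: 2/1.33 = 1.50, 2/1.53 = 1.31, 2/1.78 = 1.12.
- A 5 mg patient given placebo: 2 × 1.33 = 2.67 (K = 10), 2 × 1.53 = 3.06 (K = 30), 2 × 1.78 = 3.56 (K = 100).

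So the direction of the bias depends on the error.

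**3. Is a patient who leaves before Visit 2 in the FAS?** The passages allow two readings.

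- *In.* The protocol synopsis says "Spirometry will be repeated 1 hour" after the first dose, within 20 minutes either way; protocol 13.2.2 agrees. For spirometry, SAP 10.2.2 states that "baseline will correspond to the assessment at randomization visit (Visit 1) prior to inhalation of IMP". The one-hour value is then post-baseline, and nearly every patient with a full profile qualifies.
- *Out.* The FAS definition cites SAP 8.5, whose spirometry entry is "FEV1 % predicted, FEV1/FVC at randomization compared to Week 2, Week 4, Week 8, and Week 12", with no Day 1 post-dose value. SAP 10.4 makes the whole day of Visit 1 baseline.

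On the second reading the exit visit does not help, because protocol 13.2.5 lists neither spirometry nor SF-36 for it.

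**4. Size of that loss, on the second reading only.** The chance that at least one of the 16 patients on active treatment leaves before Visit 2 is 1 − (1 − p)^16. It is 28%, 56% and 82% for assumed exit rates p of 2%, 5% and 10%, with 16p = 0.3, 0.8 and 1.6 patients expected.

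The 95% interval for the 10 mg/5 mg ratio is the estimate multiplied and divided by exp(t × s × √(1/n1 + 1/n2)), with s = √ln(1 + CV²) and N − 3 degrees of freedom. At an assumed CV of 60%, s = 0.555. With 8 per arm the factor is exp(2.080 × 0.555 × 0.5) = 1.78. It becomes 1.82 with one active profile lost, 1.86 with one lost per active arm and 1.97 with two lost per active arm. With two lost per active arm it goes from 1.36 to 1.43 at CV 30%, and from 2.38 to 2.76 at CV 100%.

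**The case against.** **The dosing error is hypothetical.** No error is reported. Only patients are blinded (protocol 8.3.1), the first inhalation is supervised (13.2.2), and the 5 mg vials differ in cap colour and diluent volume (8.4.1). This stands and limits the likelihood. The 0 mg and 10 mg vials do share a cap colour and ampoule volume, although protocol 8.3.1 says that the strengths look different.

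**The dose ratio is unknown.** Systemic cyclosporine is permitted (protocol 10.1.2), and inhaled L-CsA is described as giving negligible serum levels (6.1.5). Background drug could bring measured ratios close to 1, where misfiling matters less. This stands, so the tables are illustrations.

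**Early leavers may already be in the FAS.** A reader might infer that the plan simply discards the profiles of patients who do not tolerate the first dose. The documents do not support that. The one-hour spirometry may count as post-baseline, the reference to SAP 8.5 may name types of measure rather than time points, and the FAS definition in protocol 14.1 carries no such reference. Patients who only stop IMP are asked to keep attending (9.3.1). Only a patient who leaves the trial before Visit 2 is in question.

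**Some BDRM exclusions suit PK too.** The SAP's own example is a patient without the condition. The PK aim concerns this patient population, so that exclusion is defensible. It does not justify every efficacy-based exclusion.

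None of this supplies a reason to group concentrations by assigned dose. The valid-case wording does not help either: it narrows the FAS, but cannot restore a patient outside it or correct a group label.

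**Conclusion.** The point holds in limited form. As written, PK follows an efficacy set grouped as randomised, and no sentence exempts it. If a dosing error occurs, exposure is reported under a dose not inhaled. With one patient misfiled between the active arms, an assumed ratio of 2 is estimated as 1.83, and after one swap as 1.68. It would be wrong to infer that every dispensing error pulls the 10 mg/5 mg ratio toward 1: a 5 mg patient given placebo moves it away.

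A valid Day 1 profile can be lost through an efficacy-based exclusion or a missing efficacy baseline. Whether it is lost on exit before Visit 2 is unsettled. The precision cost of one or two profiles is modest; possible selection related to tolerability is the better argument. The plan contains no exposure-tolerability analysis, so none can be said to be distorted.

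Severity is low to moderate: PK is a secondary, descriptive assessment, and the bias depends on events that may not occur.

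**What to change.** 1. In SAP 14.2 and protocol 14.2.5, replace the FAS by a PK set: all SAF patients with at least one evaluable post-dose cyclosporine concentration, grouped by treatment actually received. Add the set to SAP 10.2 and to the counts in SAP 11, and list the change in SAP 6.
2. Allow exclusions only for documented PK reasons (for example incomplete inhalation, or missing or mistimed samples) or absence of the target condition. Decide them at the BDRM from dosing and sampling records, not from concentrations, which could reveal the treatment.
3. State in SAP 10.2.2 whether the Visit 1 one-hour post-dose spirometry counts as post-baseline for the FAS.

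The cost is SAP and protocol wording and one analysis flag. It needs no new data, and no patient with valid PK data from the target population is lost.
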